8.3.3. Confounders and effect modifiers

The study will examine the effect of potential confounders and effect modifiers as shown in Table 2 above on the risk for outcomes of interest.

Demographic variables

- Age
- Sex
- Route of HIV Infection
- Number of years since HIV diagnosis
- Ethnic origin
- Geographic region
- Date of ART initiation

Date CAB and/or RPV LA started

Virologic variables at regimen initiation

- HIV VL at initiation of CAB LA and/or RPV LA containing regimens (and in the 12 months prior to regimen start)
 - o Continuous (copies/mL)
 - o Categorical:
 - <50 copies/mL (or < LOD in clinics where LOD > 50 copies/mL)
 - $\ge 50 \text{ to } < 200 \text{ copies/mL}$
 - $\ge 200 \text{ to } < 10,000 \text{ copies/mL}$
 - \geq 10,000 to <100,000 copies/mL
 - \geq 100,000 copies/mL

Immunologic variables at regimen initiation

- CD4 cell count at initiation of CAB LA and/or RPV LA containing regimens (and in the 12 months prior to regimen start)
 - Continuous (cells/μL)
 - o Categorical:
 - CD4 \geq 500 cells/ μ L
 - CD4 count \geq 350 to <500 cells/ μ L
 - CD4 count <350 cells/µL
- CD4 nadir prior to initiation of CAB LA and/or RPV LA based ARV regimens

Clinical variables at regimen initiation

- HIV Subtype where available
- History of previous use of integrase inhibitor-based or NNRTI-based regimen
- History of previous antiretroviral exposure
- History of previous virologic failure
- History of previous HIV drug resistance and any historical HIV-1 subtype information, where available
- Body Mass Index (BMI), height, weight
- History of AIDS-defining Events (ADE)
- Concurrent medications (Etravirine, Rifampicin, Rifapentine, Rifabutin, Ribavirin, Ketoconazole, Fluconazole, Itraconazole, Clarithromycin, Erythromycin and other medications where data are available)
- Comorbidities (all defined to be consistent with published EuroSIDA analyses)
 - o HCV co-infection [3]
 - o HBV co-infection [4]
 - o End Stage Liver Disease (ESLD) (hepatocellular carcinoma, ascites, hepatorenal syndrome, grade III/IV hepatic

- encephalopathy, unspecified liver decompensation, oesophageal variceal bleeding, liver transplantation) [3]
- Cardiovascular Disease (CVD) (myocardial infarction, stroke, invasive coronary procedure) [3]
- Chronic Kidney Disease (CKD) (confirmed [>3 months apart] eGFR <60/ml/min/1.73m² in persons with eGFR at regimen initiation ≥60/ml/min/1.73m² and confirmed 25% decline in eGFR in persons with eGFR at regimen initiation < 60/ml/min/1.73m²) [5]
- o Non-AIDS defining malignancies (NADM) (excluding hepatocellular carcinoma) [3]

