8.3.1. Exposure definitions

The study period for data collection will start at the date of initiation of oral lead-in with CAB and/or RPV. The follow-up period for data analyses will start with first injection of CAB and/or RPV LA containing regimens and end at up to 48 months after discontinuation of the last injection.

Details about use of CAB and/or RPV LA containing regimens will be collected on a separate CRF. The data collected include dates of all planned and actual injections, use of oral bridging therapy for CAB+RPV LA, HIV subtype and resistance testing prior to initiation or at time of discontinuation of LA.

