8.6. Data analysis

Between 5-10 EuroSIDA participating clinics (of 100 clinics) have a viral load measured with a limit of detection of >50 copies/ml. Individuals starting CAB+RPV LA regimen with a viral load limit of detection >50 copies/ml will be excluded from primary analyses for clinical effectiveness. We will summarise data for all other users and compare them to those included for generalisability and to help interpret the data.

AIM 1. Describe CAB and/or RPV LA containing regimens usage patterns

New users of CAB and/or RPV LA containing regimens aged >18 years will be characterized using demographics, clinical, immunologic and virologic characteristics at baseline (i.e. at initiation of regimen) stratified by different regimens noted in groups a-g above.

Individual characteristics and baseline covariates will be described using median (interquartile range [IQR]) values for continuous data and relative frequencies for categorical data. Characteristics of those starting different CAB and/or RPV LA containing regimens will be compared using chi-squared tests for categorical variables and non-parametric tests for continuous variables.

Those who start oral lead in but do not start LA regimen will be tabulated separately and demographics will be described.

AIM 2. Assess adherence, durability and discontinuation for persons starting CAB+RPV LA regimen

Individuals who receive the oral lead-in but never initiate the CAB+RPV LA regimen will be tabulated separately but not included in the primary analysis. Reasons for discontinuation will be assessed using the reasons for discontinuation as reported to EuroSIDA.

Treatment and regimen usage patterns of CAB+RPV LA regimen will be described using frequency distributions while duration of continuous treatment will be described using the mean, median, range, and standard deviation. Number of individuals with incorrect route of administration will be described.

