Descriptive analyses will compare those with and without virologic failure to assess any differences in baseline characteristics of the two groups. Detailed analysis of additional risk factors will be limited to persons with 6, 12 or 24 months of follow-up. Multivariable logistic regression models will investigate the factors associated with virologic failure at 6 months, 12 months and 24 months after CAB+RPV LA initiation. Potential explanatory variables are listed above. We will also investigate the impact of missed doses and use of oral bridging therapy by using the data collected via the CRF. Multivariate analyses will be performed when > 30 persons on CAB+RPV LA have virologic failure and analyses will be limited to persons with > 6-, 12- or 24-months follow-up. The model building strategy will follow EuroSIDA protocol and include variables significant in univariate analyses as well as *a priori* pre-specified variables of interest. Primary analysis for clinical effectiveness will include individuals on CAB+RPV LA, with VL of <50/copies/mL at regimen initiation. In addition, all the analyses will be conducted separately for individuals on CAB+RPV LA with VL of ≥50 copies/mL at regimen initiation.

Our primary analyses of virologic outcomes will censor follow-up at discontinuation of CAB+RPV LA, last visit or death, whichever occurs first, an on-treatment approach to analysis. Sensitivity analyses will use an intent to treat approach and virologic outcomes will be assessed regardless of regimen discontinuation.

We will perform additional sensitivity analysis limited to those who start CAB+RPV LA with resistance data available, to confirm no present or past evidence of viral resistance to, and no prior virological failure with agents of the NNRTI and INSTI class.

AIM 4. Monitor for resistance and next treatment response among individuals who switched off CAB+RPV LA regimen

Monitoring for resistance

Since this is a non-interventional study aiming to capture individual care in real world setting, the study will not mandate resistance testing following discontinuation of the regimen of interest. Health care providers following the local treatment guidelines decide

what laboratory and resistance tests are to be conducted. Data thus generated will be captured and analyzed by the study team.

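### Chronic kidney disease is listed as a characteristic at regimen initiation but carries a definition of new disease, so stable established disease is coded as absent

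*Protocol*

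**What the plan says.** Protocol Section 8.3.3 groups its covariates by timing. CKD appears under the heading "Clinical variables at regimen initiation", in a sub-list introduced as "Comorbidities (all defined to be consistent with published EuroSIDA analyses". Its definition has two limbs:

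- Starting eGFR 60 or above: "confirmed [>3 months apart] eGFR <60/ml/min/1.73m² in persons with eGFR at regimen initiation ≥60/ml/min/1.73m²".
- Starting eGFR below 60: "confirmed 25% decline in eGFR in persons with eGFR at regimen initiation" below 60.

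The protocol gives no other definition of CKD.

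The variable is used in two ways. Under Aim 1 in Section 8.6, new users are described by their "clinical, immunologic and virologic characteristics at baseline (i.e. at initiation of regimen". For the regression models in Aims 2 to 4, the same section says "Potential explanatory variables are listed above", which refers back to this list. Section 8.3.1 sets the time origin: "The follow-up period for data analyses will start with first injection of CAB and/or RPV LA containing regimens".

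**The concern.** A covariate at initiation should record what was true of the person by that date. This definition splits people by their eGFR at initiation and then asks for a change relative to that starting position, which is how new disease during follow-up is usually captured. Two errors follow. People whose kidney disease is established and stable at first injection do not qualify. People without it at first injection can qualify through values recorded later.

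Two results are at stake. One is the CKD row in the baseline table of a drug utilisation study, whose first aim is to describe who receives the regimens. The other is the meaning of a CKD coefficient in the models for discontinuation, non-adherence, virologic failure, resistance and next-treatment response. A covariate that can be set by data after the first injection is not a baseline predictor of events counted from that injection.

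**Working it through.** The protocol gives no figure to reproduce. The check applies the two limbs of Section 8.3.3 to example persons (the eGFR values are chosen for illustration) and sets the result against the heading.

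**Limb for starting eGFR below 60.** Read as a fall from the initiation value, the threshold is 0.75 × eGFR at initiation.

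| eGFR at initiation, stable and confirmed | Must fall to, confirmed | Coded if it stays stable |
|---|---|---|
| 59 | 0.75 × 59 = 44.25 or lower | no CKD |
| 45 | 0.75 × 45 = 33.75 or lower | no CKD |
| 30 | 0.75 × 30 = 22.5 or lower | no CKD |

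**Limb for starting eGFR of 60 or above.** A person at 80 at first injection, with two later values below 60 more than 3 months apart, meets the criterion although free of CKD at initiation.

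**Timing.** The initiation value alone classifies nobody as having CKD. If the first limb uses later values, two low values more than 3 months apart are needed, so it cannot be met until more than 3 months after the first injection. A virologic failure in month 2, which counts in the analysis of the first 6 months, would come before the covariate could be set.

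**Backward-looking reading.** The text does not contain the word after. Suppose both limbs refer to values before initiation:

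- Stable eGFR of 45: there has been no 25% decline, so still no CKD.
- First limb: it would capture only people who had a confirmed value below 60 and have since recovered to 60 or above, which is an unlikely intention.

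On either reading, confirmed and stable eGFR below 60 at initiation is coded as absence of CKD. Dependence on later values arises only on the forward reading, which is the natural one.

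**Scale, on assumptions that are not in the protocol.** Take 500 users (one of the sizes in Table 4), true confirmed CKD at initiation in 5% to 10%, and a later confirmed 25% decline in 10% to 20% of those.

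- True cases: 500 × 0.05 = 25 to 500 × 0.10 = 50.
- Coded as free of CKD: from 25 × (1 − 0.20) = 20 to 50 × (1 − 0.10) = 45.

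Under these assumptions 80% to 90% of true cases are missed. This shows the mechanism and does not estimate anything about this cohort.

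**The case against.** Several points can be made for the plan.

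- **The definitions follow published cohort analyses.** Section 8.3.3 says so and cites a source for CKD, and Section 8.5 refers to a list of clinical definitions. Neither is reproduced in the protocol. But a definition of new CKD does not measure CKD present at initiation, whatever its source, and the conflict with the heading is in the protocol's own text.
- **The heading fixes the timing, so an analyst would not use later data.** This has some force. The wording does not say that later values will be used, and the decline is not explicitly stated to be from the initiation value. It does not rescue the rule, because the backward reading also fails to identify stable CKD.
- **The effect on the models is small.** This stands. CKD is neither an outcome nor an eligibility criterion. It would enter a model only if significant in univariate analysis or pre-specified, and the multivariable failure models require more than 30 failures. With 500 users and 5% failure, a Table 4 scenario, there are 500 × 0.05 = 25 failures and no such model.

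A reader might also infer that the coding is biased against discontinuation and failure, because CKD can turn positive only in people observed long enough. The protocol does not support a direction. Sections 8.1 and 8.3.1 continue follow-up for up to 48 months after discontinuation, creatinine is routine cohort data (Table 2), and sites report everything since the last data capture each year (Section 8.5.2). The failure models are limited to people with more than 6, 12 or 24 months of follow-up. Death and loss to follow-up could still matter, but which way is not shown. For Aim 4, CKD arising between first injection and discontinuation precedes that aim's own time origin, so the dependence on future data does not apply equally to all aims.

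**Conclusion.** The point holds as a stated rule that conflicts with its own heading, not as missing detail. CKD at initiation is given an incident-event definition. People with confirmed, stable eGFR below 60 at initiation are coded as not having CKD, and on the natural reading people free of it at initiation can be coded as having it from later values. The baseline CKD prevalence in Aim 1 is therefore wrong. The candidate covariate in Aims 2 to 4 is misclassified and can depend on data after the first injection.

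It would be tempting to say that everyone with an eGFR below 60 at initiation is misclassified. That goes too far. A single unconfirmed low value does not establish CKD, and people whose eGFR later falls by a further confirmed 25% are coded as having it, although on later data.

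The size cannot be determined from the protocol, which gives neither CKD prevalence nor rates of decline. The direction of any bias is likewise undetermined. The impact is limited: one row of the baseline description is wrong for certain, and one of many candidate covariates is affected where models are fitted.

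**What to change.** In Section 8.3.3, define CKD at regimen initiation from eGFR values up to and including the date of the first injection: two values below 60 ml/min/1.73m², more than 3 months apart. Keep the present two-limb wording only for incident CKD during follow-up, if that is wanted, and label it as such.

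State how people without two such values are coded. Section 8.6, under completeness of data, allows a missing category and considers exclusion unreasonable given the few endpoints expected. A missing category fits that approach.

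The cost is a short text change and no new data collection, since serum creatinine is already routine (Table 2). The small downside is that some people will lack two eGFR values by the first injection and will be coded as unknown. Their number should be reported beside the CKD figure.

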EuroSIDA data are submitted either through the electronic case report system Research Electronic Data Capture (REDCap) or electronically using the HICDEP format. Data are handled according to above mentioned standard operating procedures (SOPs) (https://chip.dk/Studies/EuroSIDA/Study-documents). In addition, all data is pseudonymized before transfer to CHIP and is held securely. The data is held on password secured computers in London. EuroSIDA have the relevant data protection clearance, Data Protection Agency No: RH-2018-15

8.5.2. Timings of Assessment during follow-up

All sites in EuroSIDA provide follow-up information to the coordinating centre in October-December each calendar year. All relevant information for each individual occurring since last data capture is provided to the coordinating centre. For example, if a person has 3 CD4 counts measured since last data download, and started and stopped 3 ARVs for different reasons, all this information is provided rather than just the information at most recent visit. An updated version of the database is usually available for statistical analysis 6 months later, allowing the study to provide data on the individuals followed up to approximately 6-12 months prior to the close of the database.

8.6. Data analysis

Between 5-10 EuroSIDA participating clinics (of 100 clinics) have a viral load measured with a limit of detection of >50 copies/ml. Individuals starting CAB+RPV LA regimen with a viral load limit of detection >50 copies/ml will be excluded from primary analyses for clinical effectiveness. We will summarise data for all other users and compare them to those included for generalisability and to help interpret the data.

AIM 1. Describe CAB and/or RPV LA containing regimens usage patterns

New users of CAB and/or RPV LA containing regimens aged >18 years will be characterized using demographics, clinical, immunologic and virologic characteristics at baseline (i.e. at initiation of regimen) stratified by different regimens noted in groups a-g above.

Individual characteristics and baseline covariates will be described using median (interquartile range [IQR]) values for continuous data and relative frequencies for categorical data. Characteristics of those starting different CAB and/or RPV LA containing regimens will be compared using chi-squared tests for categorical variables and non-parametric tests for continuous variables.

Those who start oral lead in but do not start LA regimen will be tabulated separately and demographics will be described.

AIM 2. Assess adherence, durability and discontinuation for persons starting CAB+RPV LA regimen

Individuals who receive the oral lead-in but never initiate the CAB+RPV LA regimen will be tabulated separately but not included in the primary analysis. Reasons for discontinuation will be assessed using the reasons for discontinuation as reported to EuroSIDA.

Treatment and regimen usage patterns of CAB+RPV LA regimen will be described using frequency distributions while duration of continuous treatment will be described using the mean, median, range, and standard deviation. Number of individuals with incorrect route of administration will be described.

Non-adherence to dosing schedule will be assessed by estimating the number of individuals that missed one or more consecutive injections without taking daily oral bridging therapy or any other oral ARV regimen while not on CAB+RPV LA regimen and median number of injections missed during a 12-month period. We will also estimate the number who received the injections seven or more days later than their scheduled injection visit and median duration of delayed injections in persons using bridging therapy. In addition, the number of individuals who missed one or more consecutive injections without taking daily oral bridging therapy or those who received the injections seven or more days later than their scheduled injection visit will be assessed and patient characteristics for those individuals that are non-adherent will be described.

Logistic regression will be used to identify factors associated with not starting CAB+RPV LA in those that start lead in, to compare those missing injections where bridging treatment is used, non-adherence and to identify factors associated with discontinuation of CAB+RPV LA (when there are more than 30 endpoints). Potential explanatory variables are listed above. The model building strategy will follow EuroSIDA protocol and include variables significant in univariate analyses as well as *a priori* pre-specified variables of interest.

AIM 3. Assess the clinical effectiveness (i.e. proportion individuals experiencing virologic failure and proportion with undetectable VL) among PLWH who initiate CAB+RPV LA regimen

The study will estimate the proportion with virologic failure during the first six months and at six, twelve and twenty four months after the start of the treatment with injectable regimen. Given that this study involves persons in routine clinical care, and who may not attend clinic appointments at 6, 12 or 24 months, a window of 12 weeks around the date in question will be used for virologic failure. Thus, the proportion with virologic failure during first six months, at 6, 12 or 24 months \pm 6 weeks will be used; and if none is available, the first measurement during first six months, after 6, 12 or 24 months (and at most 6 weeks after the measurement).

Descriptive analyses will compare those with and without virologic failure to assess any differences in baseline characteristics of the two groups. Detailed analysis of additional risk factors will be limited to persons with 6, 12 or 24 months of follow-up. Multivariable logistic regression models will investigate the factors associated with virologic failure at 6 months, 12 months and 24 months after CAB+RPV LA initiation. Potential explanatory variables are listed above. We will also investigate the impact of missed doses and use of oral bridging therapy by using the data collected via the CRF. Multivariate analyses will be performed when > 30 persons on CAB+RPV LA have virologic failure and analyses will be limited to persons with > 6-, 12- or 24-months follow-up. The model building strategy will follow EuroSIDA protocol and include variables significant in univariate analyses as well as *a priori* pre-specified variables of interest. Primary analysis for clinical effectiveness will include individuals on CAB+RPV LA, with VL of <50/copies/mL at regimen initiation. In addition, all the analyses will be conducted separately for individuals on CAB+RPV LA with VL of ≥50 copies/mL at regimen initiation.

Our primary analyses of virologic outcomes will censor follow-up at discontinuation of CAB+RPV LA, last visit or death, whichever occurs first, an on-treatment approach to analysis. Sensitivity analyses will use an intent to treat approach and virologic outcomes will be assessed regardless of regimen discontinuation.

We will perform additional sensitivity analysis limited to those who start CAB+RPV LA with resistance data available, to confirm no present or past evidence of viral resistance to, and no prior virological failure with agents of the NNRTI and INSTI class.

AIM 4. Monitor for resistance and next treatment response among individuals who switched off CAB+RPV LA regimen

Monitoring for resistance

Since this is a non-interventional study aiming to capture individual care in real world setting, the study will not mandate resistance testing following discontinuation of the regimen of interest. Health care providers following the local treatment guidelines decide

what laboratory and resistance tests are to be conducted. Data thus generated will be captured and analyzed by the study team.

Descriptive statistics will describe and compare the ARV regimen individuals are switched to after discontinuation of CAB+RPV LA regimen. As resistance testing will not be common, we will describe the characteristics of those with and without resistance testing at virologic failure and again at virologic failure during the 12, 24, 36 and 48 months after switching regimens and use logistic regression to identify factors associated with resistance testing. Where more than 1 resistance test is available during the 12, 24, 36 and 48 months after stopping CAB+RPV LA regimen, cumulative resistance data will be collected and reported.

Study will monitor for resistance at virologic failure and again at virologic failure during the 12, 24, 36 and 48 months following the switch, where resistance data are available. Resistance patterns in those with resistance testing will be summarized. Depending on the number of resistance tests performed and amount of resistance detected, logistic regression will be used to identify factors associated with resistance to CAB+RPV LA. Potential explanatory variables are listed above including missed and delayed doses and use of bridging therapy.

Next treatment response

The study will describe virologic success at 12, 24, 36 and 48 months after discontinuation of CAB+RPV LA regimen, using virologic failure definition as described above. Given that this study involves persons in routine clinical care, and who may not attend clinic appointments every 12 months, a window of 12 weeks around the date in question will be used for virologic testing data. Thus, the proportion with virologic success at 12, 24, 36 and 48 months \pm 6 weeks will be used; and if none is available, the first measurement after 6 or 12 months will be used.

Descriptive analyses will compare those with and without virologic success at 12, 24, 36 and 48 months after stopping the CAB+RPV LA regimen, as well as the next regimen started and time to start the next regimen following discontinuation of the regimen. If numbers allow for further analyses, multivariable logistic regression models will investigate the factors associated with virologic success at 12, 24, 36 and 48 months after switching off CAB+RPV LA regimen. Potential explanatory variables are listed above. Multivariate analyses will be performed when > 30 persons in the relevant treatment group have virologic success and analyses will be limited to persons with > 12 months follow-up. The model building strategy will follow EuroSIDA protocol and include variables significant in univariate analyses as well as *a priori* pre-specified variables of interest.

AIM 5. Evaluate the effectiveness of routine risk minimisation measures for regimen adherence, discontinuation due to incorrect route of administration and off-label use of CAB+RPV LA regimen

The purpose of this aim is to monitor to see if label guidance is adhered to, off label usage, adherence and discontinuation due to incorrect route of administration. This analysis on effectiveness of routine risk minimisation measures will be stratified for each region in the Eurosida cohort.

Analysis of off-label users – regimen combinations other than CAB+RPV LA (b -g in objective 1)

Descriptive Analysis:

As noted in Aim 1 above, analysis will be performed on the off-label users of CAB and/or RPV LA containing regimens. They will be characterized using demographics, clinical, immunologic and virologic characteristics at baseline (i.e. at initiation of regimen) stratified by different regimens noted in groups b-g above.

Adherence and Discontinuation:

Non-adherence to the dosing schedule and discontinuation due to incorrect route of administration will be assessed as described under Aim 2.

Clinical Outcomes:

Analysis will be conducted for the off-label users of CAB and/or RPV LA containing regimens separately to assess clinical outcome similar to description under Aim 3 above.

Descriptive analyses will compare those with and without virologic failure to assess any differences in baseline characteristics of the two groups. Multivariable logistic regression models will investigate the factors associated with virologic failure at 6 months, 12 months and 24 months after regimen initiation. We will also investigate the impact of missed doses and use of oral bridging therapy by using the data collected via the CRF Multivariate analyses will be performed when > 30 persons on the regimen of interest have virologic failure and analyses will be limited to persons with > 6-, 12- or 24-months follow-up.

Depending on the numbers, additional analysis stratifying by VL at regimen initiation (<50 copies/mL and ≥50 copies/mL) will be conducted. We will perform additional sensitivity analysis limited to those who start one of the other regimens with resistance data available, to confirm no present or past evidence of viral resistance to, and no prior virological failure with agents of the NNRTI and INSTI class.

Completeness of data

Not all variables within EuroSIDA are complete for all persons; missing data is rarely missing at random from observational cohort studies. Data may be categorized, including a category for missing, persons may be completely excluded with missing data, or imputation can be used. None of these approaches is likely to be unbiased, but with a small number of primary endpoints anticipated, excluding those with missing data would not be a reasonable approach to analysis.

